10.2 Possible undesirable effects

Serious adverse effects are highly unlikely.

- The acquisition is not painful but requires participants to remain as motionless as possible for up to 50 minutes.
- Virtual Reality setup may induce momentary dizziness.

10.3 Intervention arms

Experimental: BCI intervention

This group will undergo seven sessions of BCI intervention. Each subject will also undergo neuropsychological evaluations and "Joint-attention task" before the first BCI session (week 0) and after the last BCI session (week 16). The first four sessions are weekly while the other three are monthly. The intervention will take a total of four months.

10.4 Brain area/s of interest

Brain areas of interest include the parietal lobe of the brain because P300 has been classically reported as an enhanced positive-going component with a centro-parietal scalp distribution that is maximal over midline scalp sites. This way EEG electrodes of BCI will be strategically placed in the central, parietal and occipital electrodes positions (following the international 10-20 system), specially over the midline positions.

10.5 Adherence

Adherence is defined as attending all seven BCI sessions.

After the enrolment, the participant will be given a schedule with the sessions plan. Additionally, the participant or caregiver will be reminded of each session by telephone-call one week earlier and by message the day before.

On the basis of following the study protocol, follow-up plan should depend on specific situation of participants such as avoiding the holiday or the inconvenient day. When the intervention is over, researchers should remind patients of the next appointment time. For eventual absent participants, researchers should do telephone interviews in time, ask the reason and try to reschedule.

11 Outcome measures

11.1 **Primary outcome measure**

The results [Number of items of social attention that a patient can accurately identify in the avatar's action, e.g. looking at, pointing at] in a separate "Joint-attention task" will be the primary outcome measure. The experimental group will be evaluated in the pre and post evaluation time with this test.

11.2 Secondary outcome measures

Secondary outcomes comprise the core measures detailed in Table 1 below.

- The results in Autism Treatment Evaluation Checklist (ATEC) [Sociability and Cognitive Awareness Subtests] will be one of the secondary outcome measures. The group will be evaluated in the pre and post evaluation time with this test.

- The results in Vineland Adaptive Behavior Scale (VABS) [Socialization and Daily Living Skills Domains] will be one of the secondary outcome measures. The group will be evaluated in the pre and post evaluation time with this test.

| Measure | Outcomes | Description | Timepoint |
|--|--|---|-----------|
| Demographic questionnaire | Age, gender, education, SES | | Baseline |
| Thought control questionnaire (TCQ)(Wells & Davies, 1994) | Thought control (distraction, punishment, worry; re- appraisal; social control) | 30-item measure to assess effectiveness of strategies used for the control of unpleasant/unwanted thoughts | Baseline |
| Thought control ability questionnaire (TCAQ)(Lucia no et al., 2005) | Thought control | 25-item measure of individual differences in perceived ability to control unwanted & intrusive thoughts | Baseline |
| Wechsler Adult Intelligence Scale (WAIS- III)(Wechsler , 1997) | IQ | Global intelligence/IQ measure | Baseline |

Table 1. Other BRAINTRAIN core outcomes

| Profile of Mood States (POMS)(Heuc hert and McNair, 2012) | Anger; confusion; depression; fatigue; tension and vigour | | Pre-post assessment (each session) |
|---|--|--|--|
| Hospital Anxiety & Depression Scale (HADS)(Zigm ond and Snaith, 1983) | Anxiety; depression | 24-item scale (7 depression & 7 anxiety items) | Pre-post assessment (across intervention) |
| Beck Depression Inventory (BDI-II)(Beck et al., 1996) | Depression | 21-item measure of clinical depression | Pre-post assessment (across intervention) |
| Autism Treatment Evaluation Checklist (ATEC) (Rimland and Edelson, 1999) | Autism Traits | 77-items: speech/language/commu nication (14 items); sociability (20 items); sensory/cognitive awareness (18 items); health/physical/behaviour (25 items) | Pre-post assessment (across intervention) |
| Vineland Adaptive Behaviour Scales (VABS) (Sparrow et | Adaptive Behaviour | 297 items measure of adaptive behaviour Three main domains: Communication (COM), Daily Living Skills (DLS) and Socialization (SOC) | Pre-post assessment (across intervention) |

| al., 1984) | and total score, the Adaptive Behaviour Composite (ABC) | |
|--|---|--|
| Debriefing interview questionnaire | Covers: strategies; general experience of the process; adverse effects; awareness of group allocation | Post- assessment (ideally each session) |

12 Study procedures

12.1 Data collection

Each BCI session consists of selecting targets of social cues through an oddball paradigm designed in a virtual reality scenario. The BCI virtual reality scenario will be presented via Oculus Rift DK2. The EEG acquisition will be made via EEG electrodes placed on participant's head using an EEG cap. The task was initially thought to be based on mentally counting how many times a virtual human character directs its attention (gaze) to a specific object in the scene. Based on a pilot study the task is to mentally count the blinks of the object to which the virtual human character directed its attention (gaze) at the beginning of each run. The computer reads/stores the EEG signal and detects if the subject was counting the correct object via detection of P300 elicited by the target object blink. Each session is composed by the following steps:

- Subject and BCI setup preparation (10 minutes)
 - Explain the task to participant;
 - Place the cap with electrodes on participant's head;
 - Check EEG signal quality.
- Data Acquisition (up to 40 minutes)
 - BCI Training phase ~ 20 minutes;

• BCI Testing – 5 minutes (single trial classification) to 20 minutes (ten trials classification). The number of trials needed to validate depends on a predefined accuracy (equal for every subject). Subjects may need different number of trials to achieve this accuracy, thus the higher the number of trials, the longer the experiment is. The task consists in the presentation of 50 target events

The sessions will be controlled by the EEG technician responsible for the BCI interventions of the BrainTrain research team at UCo.

All data collected from training and testing phases will be stored in digital format inside the stimulation machine. Upon concluded the session, data will be copied into a hard-drive for posterior analysis.

Stored data will be processed and analysed by the BrainTrain research team at UCo.

Personal identification of each participant will be hidden. Unique ID will be used to identify each participant's data for the whole course of the clinical trial and future references.

12.2 Screening

Not applicable.

12.3 Pre-test

The experimental group will undergo an initial diagnostic and neuropsychological evaluation, followed by a customized "Joint-attention" assessment test and Autism Treatment Evaluation Checklist (ATEC) [Sociability and Cognitive Awareness Subtests], Vineland Adaptive Behaviour Scale (VABS) [Socialization and Daily Living Skills Domains].

12.4 Post-test

Once concluded the intervention, the group performs the a posteriori evaluation, to assess the hypothesized improvements on the measures, as compared to pre-test assessment.

12.5 Follow-up

We will perform a final follow-up 6 months after the intervention. Not applicable otherwise.

12.6 Samples & storage

Not applicable.

12.7 Facilities & equipment

BCI sessions will be carried out in spacious and quiet room with minimal electrical interference. The room must have at least one table and one chair.

The BCI acquisition module consists of a cap with eight active electrodes that will be placed in the head of participant. The electrodes are connected to g.tec amplifier that sends the data wirelessly for the computer.

The computer contains the data processing module (Matlab) and the virtual-reality module (Vizard).

The BCI loop is closed with the Oculus Rift DK2 (Oculos VR, Inc), placed on participant's head.

12.8 Incidental findings

Not applicable.

13 Statistical considerations

13.1 Randomisation

Not Applicable

13.2 Sample size

Considering the longitudinal design proposed, with alpha 0.05, power of 80%, and standardized effect of 0.8 (improvement of 8 points for and estimated SD of 10 points) we would need 15 subjects (plus 3 in case of drop outs). We will add three additional subjects to account for drop-offs. The sample size calculations were performed based on a matched 2 sided paired t-test. To determine these values we used the G*Power tool (Faul et al., 2007). The sample size calculations were performed under the assumption that the distribution of the mean differences is normal. Similarly, without the normality assumption, we would also need 15 subjects, considering a non-parametric Wilcoxon test.

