4.2 Rationale for current study

The main hypothesis is that training of initiation and response to joint attention cues using gaming/BCI interfaces can be used to improve joint attention social cognition skills in ASD participants.

The BCI setup will be used to train initiation and repeated responses to a joint attention object. An independent game platform will be used to test whether enhanced rates of joint attention (initiation and responses) were achieved.

This study aims to demonstrate that improvements in identification of social cues (and improvement of overall social behaviour) in subjects with ASD can be achieved using social games together with a BCI setup. The primary goal is to ensure increased rate of responses to joint attention cues.

To evaluate the improvements, we will use a new task/realistic game that will challenge the detection of initiation of joint attention cues (from avatars – gaze or pointing). The number of correct responses (to particular objects and not to non-object parts of the scene, will be recorded). We will also record incorrect responses to non-pointing body gestures. Participants will be challenged with about 20 events per minute (one every three seconds), of variable degree of difficulty. Given that the experiment lasts 10 minutes, and some events are control measures, we will have a total of 150 test events and 50 control events. We expect that ASD subjects will be able to correctly report a mean of 75 of the target events, based on tailored task difficulty.

Considering the longitudinal design proposed, with alpha 0.05, power of 80%, and standardized effect of 0.8 (improvement of 8 points for an estimated SD of 10 points) we would need 15 subjects. We will consider three additional subjects to account for drop-offs. The sample size calculations were performed based on a matched 2 sided paired t-test. To determine these values we used the G*Power tool (Faul, Erdfelder, Lang, & Buchner, 2007). The sample size calculations were performed under the assumption that the distribution of the mean differences is normal. Without the normality assumption, we would also need 15 subjects, considering a non-parametric Wilcoxon test.

The structure proposed for this study is the following: (1) initial eligibility screening, (2) preintervention, (3) intervention process, (4) post-intervention, and (5) follow-up.

5 Study objective(s)

5.1 **Primary objective(s)**

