3.3 SAMPLE SIZE

To determine de sample size, we used the G*Power tool (Faul, Erdfelder, Lang & Buchner, 2007):

Test family: t-test;

Statistical test: Means (difference between two different means);

Type of power analysis: A priori; Fixed input parameters: Tail(s): Two;

α err prob: 0.05;

Output: Estimated sample size

		Effe	ect Siz	e dz (ES)
		0.8	0.9	1.0	1.1
	0.7	12	10	9	8
Power	0.8	15	12	10	9
	0.9	19	16	13	11

with
$$ES = Cohen's \ dz = \frac{M_{diff}}{\sqrt{\frac{\sum (x_{diff} - M_{diff})^2}{N-1}}}$$
. Based in other effects described in the literature, the effect

size considered is 0.8 (the means difference is 0.8 standard deviations). In these conditions, for power of 0.8 the estimated sample size is 15.

Without the normality assumption of the distribution of the means differences, we would also need 15 subjects, considering a non-parametric test.

Assuming a 20% dropout rate (based on literature) the sample size will be 18.

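### The Wilcoxon sample size of 15 is stated as free of normality, but exactly 15 results only if the differences are normal; otherwise power at 15 depends on their shape

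*Protocol*

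**What the plan says.** Protocol 13.2 sets the size "with alpha 0.05, power of 80%, and standardized effect of 0.8", the effect being an "improvement of 8 points for and estimated SD of 10 points". The calculation is "based on a matched 2 sided paired t-test", run in G*Power, and "performed under the assumption that the distribution of the mean differences is normal". This gives 15.

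The section then says that, "without the normality assumption, we would also need 15 subjects, considering a non-parametric Wilcoxon test". Protocol 4.2 has the same sentence: "Without the normality assumption, we would also need 15 subjects, considering a non-parametric Wilcoxon test". SAP 3.3 repeats it: "Without the normality assumption of the distribution of the means differences, we would also need 15", there with reference only to a non-parametric test.

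Neither document states which parent distribution or efficiency setting produced this second 15. Three further subjects are added for dropout, giving 18; SAP 3.3 ties this to an assumed 20% dropout rate.

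The fallback is used when normality is not accepted (Protocol 15.1; SAP 6.3.4). SAP 6.3.3 names the Shapiro-Wilk test for that check, and SAP 6.3.4 lists Friedman, Wilcoxon or Sign tests as the alternatives.

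**The concern.** The power of a signed-rank test at a given standardized effect is not fixed until something is said about the shape of the differences. A sample size described as free of the normality assumption must therefore rest on some other shape, or on a bound. The documents give neither, and the same integer as for the t-test suggests that a normal parent was kept.

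The non-parametric test is meant for the case where normality has been doubted, so a figure that depends on normality does not describe that case. A reader would conclude that switching tests leaves 80% power at 15 whatever the shape. The plan does not show that.

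**Working it through.** **Inputs.** From Protocol 13.2: two-sided alpha 0.05, target power 80%, dz = 8/10 = 0.8, G*Power. The ARE constants for the signed-rank test relative to the t-test are not in the documents and are taken as standard values: normal 3/π = 0.955, logistic π²/9 = 1.097, Laplace 1.5, minimum 0.864. It is also an assumption that G*Power's ARE method was used.

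**Step 1: the t-test figure.** Power comes from the noncentral t with df = n − 1 and noncentrality 0.8√n. At n = 14 it is 79.0%; at n = 15 (df 14, noncentrality 3.098) it is 82.1%. The required n is 15, as stated. All 12 cells of the SAP 3.3 table also reproduce.

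**Step 2: the Wilcoxon figure.** Replace n by n × ARE, so df = n·ARE − 1 and noncentrality = 0.8√(n·ARE).

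- Normal parent, n = 15: 15 × 0.955 = 14.32, df 13.32, noncentrality 3.028, power 80.07%. At n = 14 it is 76.8%.
- Minimum ARE, n = 15: 15 × 0.864 = 12.96, df 11.96, noncentrality 2.880, power 75.3%. At n = 16 it is 78.4%; at n = 17 (effective 14.69, noncentrality 3.066) it is 81.2%.

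| Setting | n for 80% | Power at n = 15 |
|---|---|---|
| Normal | 15 | 80.07% |
| Logistic | 14 | 85.9% |
| Laplace | 10 | 95.2% |
| Minimum ARE | 17 | 75.3% |

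Only the normal parent returns exactly 15. A one-sided test would need 12 (normal) or 13 (minimum ARE), so sidedness does not explain the figure.

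**Step 3: check without the approximation.** The exact signed-rank test was simulated at n = 15 and dz 0.8, with 40,000 replicates per shape. It rejects when the smaller rank sum is 25 or less, an actual size of 0.048.

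| Shape of differences | Simulated power |
|---|---|
| Normal | 80.1% |
| Uniform | 74.3% |
| Parabolic (the minimum-ARE shape) | 76.6% |
| Logistic | 82.6% |
| Laplace | 84.5% |
| t(5) | 85.5% |
| Strongly bimodal | 68.0% |

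Repeat runs moved these figures by less than one percentage point where a shape was rerun. The ARE method is optimistic for heavy tails at this n (Laplace 95.2% against 84.5%), but the direction is the same: light-tailed shapes fall below 80% and symmetric heavier-tailed shapes lie above it.

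**Step 4: enrolment.** At the SAP's 20% dropout, 18 × 0.8 = 14.4 expected completers. Securing 17 would take 17/0.8 = 21.25, so 22 recruited.

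**The case against.** The strongest reply is that 15 reproduces and is not an arithmetic slip: the two-sided Wilcoxon calculation with a normal parent gives 80.07%. Dropping normality does not select the worst case either, since 15 is more than enough for logistic, t(5) and Laplace differences. All of this stands. What it leaves untouched is that the condition written beside the number is not the condition that produces it.

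A second reply concerns relevance. In simulation at n = 15, Shapiro-Wilk rejected the parabolic shape in only 4.6% of samples, about the nominal rate, but Laplace in 21%. The shape behind the 17 would therefore seldom reach the Wilcoxon test. This limits the practical effect, and it is a reason not to treat 17 as the true requirement. It does not make the sentence right: strongly bimodal differences are often rejected and have power well below 80%.

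Third, the gap is two subjects in a single-arm study that SAP 6.1 calls a feasibility trial, and the assumed effect of 0.8 matters more than the efficiency setting. That is fair and is why the point is minor.

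A reader might go further and infer that, without normality, 17 are needed and 15 guarantee 75%. The material does not support that. The 0.864 bound is asymptotic and holds for symmetric shapes, and the simulations gave 74.3% for uniform and 68.0% for strongly bimodal differences. The minimum-ARE figure is a conservative benchmark. It is neither a floor at n = 15 nor free of assumptions.

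**Conclusion.** Wrong as written, minor. The unconditional claim in Protocol 4.2 and 13.2 and SAP 3.3 is supported only for normal differences, and there with almost no slack. For other shapes, 15 may give less than 80% (about 75% under minimum ARE, about 74% to 77% in exact simulation for uniform or parabolic differences) or more (symmetric heavier tails). The documents give no data on the shape of the differences, so neither case can be excluded.

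The conclusion assumes the standard ARE constants and a standardized effect of 0.8 for every shape. That a normal parent was used is an inference from the match, since the documents do not say so. The t-test sample size is unaffected, and the point does not show that enrolment must rise.

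**What to change.** In Protocol 4.2, Protocol 13.2 and SAP 3.3, replace the sentence with:

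> *15 subjects give about 80% power for the Wilcoxon signed-rank test if the differences are normal. For non-normal differences the power depends on shape; under the minimum-ARE setting (symmetric shapes, asymptotic) 15 completers give about 75%, and 17 would be needed for 80%.*

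This also names the test in SAP 3.3, which now leaves it open. The minimum-ARE figure should not be called a guarantee or assumption-free.

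Planned enrolment of 18 can stay, with the lower power stated. The three extra subjects are the dropout allowance, so recruiting 18 does not secure 17 completers. The cost is one sentence in three places and a slightly less favourable stated figure; no analysis changes.

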13.3 Missing, unused & spurious data

Detail provided in the Statistical Analysis Plan (SAP).

13.4 Procedures for reporting deviation(s) from the original SAP

These will be submitted as substantial amendments where applicable and recorded in subsequent versions of the protocol and SAP.

13.5 Termination of the study

Reasons for early termination of the study include unexpected, unacceptable side effects.

14 Adverse Events

14.1 **Definitions**

Adverse Event (AE): Any untoward medical occurrence in a participant which does not necessarily have a causal relationship with this treatment. An AE can therefore be any unfavourable and unintended sign (including abnormal laboratory finding), symptom, or disease.

Serious Adverse Event (SAE): Any adverse event that:

- Results in death
- Is life-threatening*
- Required hospitalisation or prolongation of existing hospitalisation**
- Results in persistent or significant disability or incapacity
- Consists of a congenital anomaly or birth defect
- Other medically important condition ***

* Note: The term "life-threatening" in the definition of serious refers to an event in which the participant was at risk of death at the time of the event; it does not refer to an event which hypothetically might have caused death if it were more severe.

** Note: Hospitalisation is defined as an inpatient admission, regardless of the length of stay, even if the hospitalisation is a precautionary measure, for continued observation. Pre-planned hospitalisation e.g. for pre-existing conditions which have not worsened or elective procedures does not constitute an adverse event.

*** Note: other events that may not result in death are not life-threatening, or do not require hospitalisation may be considered as a serious adverse event when, based upon appropriate medical judgement, the event may jeopardise the participant and may require medical or surgical intervention to prevent one of the outcomes listed above.

14.2 Causality

The assignment of causality should be made by the Investigator responsible for the care of the participant.

Table 2. Causality

| Relationship | Description |
|--------------|-------------|
| | |

| Unrelated | There is no evidence of any causal relationship with the study or |
|------------|---|
| | intervention. |
| | |
| Unlikely | There is little evidence to suggest there is a casual relationship (e.g. |
| | the event did not occur within a reasonable time after intervention) |
| | with the study or intervention. There is another reasonable |
| | explanation for the event (e.g. the participant's clinical condition, |
| | other treatment). |
| | |
| Possible | There is some evidence to suggest a causal relationship with the study |
| | or intervention (e.g. because the event occurs within a reasonable |
| | time after intervention). However, the influence of other factors may |
| | have contributed to the event (e.g. the participant's clinical condition, |
| | other treatments). |
| | |
| Probable | There is evidence to suggest a causal relationship and the influence of |
| | other factors is unlikely. |
| | |
| Definite | There is clear evidence to suggest a causal relationship and other |
| | possible contributing factors can be ruled out. |
| Not | There is insufficient or incomplete evidence to make a judgement of |
| | |
| assessable | the causal relationship. |
| | |

14.3 Expectedness

The assessment of whether or not an SAE is an expected consequence of receiving the intervention will be provided by the Lead Researcher.

Depending on the nature of the event, the reporting procedures outlined in this protocol should be followed. Any queries concerning adverse event reporting should be directed to [name] - Principal investigator.

14.4 Reporting procedures

14.4.1 Events exempt from reporting (non-serious AEs)

All such events, whether expected or not, should be recorded on the relevant case report form.

An SAE form should be completed for all SAEs within 24 hours. Events exempt from SAE reporting are set out in Table 2 and information relating to them should instead be captured on the relevant CRF.

| Adverse Event | Information |
|---------------|---|
| Nausea | Immersive Virtual Reality setup may induce momentary nausea to the participants. |
| Discomfort | EEG cap and electrodes, as well as Virtual Reality setup may cause discomfort to the participants |

Table 3. Adverse Events exempt from reporting

Additional information should be sent within 5 days if the event has not resolved at the time of reporting. All events should be followed up through to resolution.

In the case of serious, unexpected and related adverse events, the procedures will be taken as referred in the Informed Consent Form. This document can be found attached in the appendices.

